6.5 Criteria for Removal from Study

Patients will be removed from study when any of the criteria listed in Section 6.4 apply. The reason for study removal and the date the patient was removed must be documented in the Case Report Form.

6.6 Correlative Studies

6.6.1 Baseline and longitudinal laboratory assessment (Appendix 2). Appendix 2 contains data elements that will be collected at both baseline and every three days while the patient is hospitalized.

7.0 PROCEDURES FOR PATIENT ENTRY ON STUDY

7.1 Informed Consent

The patient or legal surrogate must be aware of the nature of his/her disease and willingly consent after being informed of the procedure to be followed, the experimental nature of the therapy, alternatives, potential benefits, side effects, risks, and discomforts. Human protection committee approval of this protocol and a consent form is required.

Whenever possible, the clinician or other delegated staff will obtain informed consent in person. In the event PPE preservation is needed, we will use the process outlined below.

Consent Process for Hospitalized COVID-19 Positive Patients in Isolation

- Once a potential subject is identified, the PI will speak with the treating clinician. The clinician will tell the patient that they may be eligible for a trial and that someone from the research team would be calling them.
- Someone from the study team will speak with the patient to introduce the study and assess their initial interest (via phone call/facetime/zoom if the patient has access).
- If patient is interested in learning more about the study, the study team would email the consent form to the patients' nurse to print out and take to the patient to read the next time she/he enters the room.
- Research staff (delegated to conduct consent) will have another discussion with the patient via phone (or facetime/zoom) to review the consent form, answer the patient's questions and obtain verbal consent.
- If the patient has a phone with a camera in their hospital room, they can print their name, sign and date the subject lines of the consent document, take a picture of the signed page and email it to the research staff.
- If the patient does not have a phone camera in their room to take a picture of the signed consent document, a witness (unit nurse ideally) would need to be present in the room or on a three way phone call to attest that the consent was reviewed with the patient, the patient had an opportunity to ask questions and they agree to consent to participate in the study.
- Due to isolation precautions, the consent will remain with the patient and not be removed from the room. Upon patient discharge the consent form will be destroyed.
- The witness will sign a copy that has not been taken in the room, take a picture or scan a copy of the signature page and send via email to the research staff.
- The independent witness will document in EPIC his/her participation in the consent process.
- The research team should document the consent process in EPIC, sign as the person obtaining consent and upload a copy of the signed consent under the media tab.
- The research team should document the entire consent discussion in EPIC including questions that the patient asked and how understanding was assessed.
- When the patient is discharged, the research staff can mail a partially signed ICF document to the home of the patient when they are discharged home.

Consent process for hospitalized COVID-19 positive patients in isolation – When LAR is needed

- If a patient is on the ventilator and unable to provide consent, the patients' LAR can consent on their behalf following the LAR consenting process.

- If the LAR is not able to meet with the research team for the consent discussion due to their own quarantine or visitors being prohibited. The research team will have the option to email the consent to the LAR for their review.
- The research team will review the document with the LAR over the phone, answer all questions and assess understanding prior to obtaining signature.
- The LAR can sign and return the signed page by taking a photo or scanning and then emailing to the research team. Due to isolation precautions, the consent will remain with the LAR and not be returned. If, due to technology limitations, it is not possible for the LAR to receive the consent via email, print, sign electronically, or take an image of the consent form, the LAR may provide consent with a witness signing the consent.
- The research team will then sign as the person conducting consent send a signed copy to the LAR.
- The research staff will document the entire LAR consent process in EPIC
- The site will request a waiver of authorization from the IRB until the patient is able to sign the consent and authorization for themselves.

7.2 Eligibility Checklist

The Investigator and study personnel are required to complete the eligibility checklist and ensure that there is adequate source documentation regarding eligibility. In the event that there is no written confirmation that a patient meets a criterion, the Investigator must document eligibility in patient's chart.

8.0 DOSE MODIFICATION FOR OBESE PATIENTS

There is standard dose of 1 unit (approximately 200 mL) convalescent plasma for all patients.

9.0 CRITERIA FOR RESPONSE ASSESSMENT

All patients will be evaluated for response based on clinical outcomes and laboratory improvement.

Clinical assessment is done daily. Laboratory evaluation is done every three days.

10.0 MONITORING OF PATIENTS

Baseline evaluations are to be conducted the day of planned plasma infusion. At the discretion of the treating team, convalescent plasma may be held.

The recipient will be monitored for transfusion reaction in accordance with Norton Healthcare's policy which includes:

- Take vital signs (temp, pulse, blood pressure) prior to, 15 minutes after initiating and at the completion of the transfusion.
- RN, LPN, APRN, PA must remain with the patient unit the 15 min vital signs are performed and asses the patient periodically during the transfusion.

- Follow Norton Healthcare policy for Transfusion Reaction Protocol. Transfusion reactions will be reported per institutional policy.

Physical examination/clinical assessment will be done each day while on study.

Imaging will be completed at the discretion of the treatment team in response to clinical needs.

Laboratory testing as listed in Appendix 1 should be repeated every three days as part of clinical care. The frequency of overall testing should be at the discretion of the treating team.

Physical examination and laboratory recording should continue until patient no longer actively followed per section **6.4** and **6.5**.

11.0 STATISTICAL CONSIDERATIONS

11.1 Study Design / Endpoints

This study uses a standard descriptive statistics for outcomes.

To determine the therapeutic efficacy (response rate) of convalescent plasma infusion in patients at high risk for mortality when infected by SARS-CoV-2 (COVID-19). The primary endpoint will be determined as prevention of progression to severe or life threatening COVID-19 during the current hospitalization. The primary endpoint will be assessed at discharge and by evaluating if the patient experienced the following data elements: respiratory rate $>30/\text{min}$, Blood oxygen saturation $<93\%$, partial pressure of arterial oxygen to fraction of inspired oxygen ration <300 , or received a medical diagnosis of respiratory failure, septic shock or multiple organ dysfunction/failure. This will be captured from the daily physical exam/clinical assessment done as part of routine care. See table 1.

The secondary objectives are to:

- Determine the immunologic effects of convalescent plasma infusion as measured by serial SARS-CoV-2 Ag levels through RT-PCR. This will be measured by CoV PCR collected at enrollment, day 7 and discharge.
- To measure normalization of laboratory parameters for risk as referenced in Appendix 2. Lab values outlined in appendix 2 will be documented every 3 days while the patient is hospitalized and we will evaluate labs from the time of convalescent plasma infusion to the time that lab value returns to within the institution's normal range.

11.2 Sample Size and Accrual Rate

The maximum projected accrual is 100 patients. Patients who succumb to COVID-19 or associated comorbid illness will be clearly identified. Patients who die as a result of the convalescent plasma infusion, though likely rare, will result in mandatory study suspension until review undertaken.

Summary statistics will be calculated: mean and standard deviation for continuous variables; frequency for categorical variables. No inferential statistical tests of hypotheses are planned. For exploratory purposes, standard statistical method will be used. For repeated measures over time, individual as well as group profile plots will be generated to visualize the data.

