1.2 Secondary Objectives

- 1.2.1 To determine the immunologic effects of convalescent plasma infusion as measured by serial SARS-CoV-2 Ag levels through RT-PCR. This will be measured by CoV PCR collected at enrollment, day 7 and discharge.
- 1.2.2 To measure normalization of laboratory parameters for risk as referenced in Appendix 2. Lab values outlined in appendix 2 will be documented every 3 days while the patient is hospitalized and we will evaluate labs from the time of convalescent plasma infusion to the time that lab value returns to within the institution's normal range.

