6.4 Duration of Therapy

Patients should be considered enrolled in this clinical trial until discharge from the hospital or the following:

- Unacceptable adverse event(s),
- Patient decides to withdraw from the study, or
- General or specific changes in the patient's condition render the patient unacceptable for further treatment in the judgment of the investigator.

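### The lab-normalisation objective has no stated outcome or denominator; read as a time, its mean and SD would cover only patients seen to normalise in hospital

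*Combined protocol and SAP*

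**What the plan says.** - **Outcome.** Sections 1.2.2 and 11.1 describe normalisation of the Appendix 2 labs, evaluated "from the time of convalescent plasma infusion to the time that lab value returns to within" the institution's normal range.
- **Schedule.** "Lab values outlined in appendix 2 will be documented every 3 days while the patient is hospitalized" (11.1). Section 6.6 agrees: "Appendix 2 contains data elements that will be collected at both baseline and every three days while the patient is hospitalized". Section 10.0 puts the baseline evaluation on the day of planned infusion and adds: "The frequency of overall testing should be at the discretion of the treating team".
- **End of observation.** "Patients should be considered enrolled in this clinical trial until discharge from the hospital or the following" (6.4): an unacceptable adverse event, withdrawal, or a change in condition as judged by the investigator. Section 10.0 ties labs to the same point: "Physical examination and laboratory recording should continue until patient no longer actively followed per section" 6.4 and 6.5. No lab after discharge is planned.
- **Analysis.** "Summary statistics will be calculated: mean and standard deviation for continuous variables; frequency for categorical variables" (11.2). The same section rules out hypothesis tests, offers individual and group profile plots for repeated measures, and allows an unnamed standard method for exploration. Deaths are to be flagged, but 11.2 does not say how they enter the lab outcome.
- **Response.** "All patients will be evaluated for response based on clinical outcomes and laboratory improvement" (9.0).

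**The concern.** An interval that starts at infusion and ends when a marker is back in range is a time to event. It can be observed only while the patient is in hospital and having labs. A patient who dies, goes home or is removed with the marker still abnormal has no such time, and the plan assigns none. If the stated mean and SD are applied to this interval, the patients without an observed time drop out. The result then reflects how long patients stayed as well as how fast the marker cleared, and deaths without normalisation leave no trace in it. With no control arm and no tests, the descriptive summaries are the whole result for this objective, and a reader could take such a mean as the time to normalisation after plasma.

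**Working it through.** **1. Figures in the plan.** There is none to reproduce. The only design figure is the accrual cap of 100, which is not in dispute. The documents give no time to normalisation, length of stay or death rate, so every input below is an assumption.

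**2. Who can contribute.** Let T be the days from infusion to normalisation and C the days to the end of lab recording. With labs every 3 days, normalisation is first seen at G = 3 × ceil(T/3), and only if G ≤ C. Without a rule that gives the others a value, the only mean available is that of G among patients with G ≤ C.

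**3. Hand check (continuous time, T and C independent exponentials).** Put a = ln 2 / median T and b = ln 2 / median C. Then the true mean is 1/a, the proportion seen is a/(a+b), and the mean among those seen is 1/(a+b).
- Both medians 7 days: a = b = 0.693/7 = 0.099. True mean 10.1 days; proportion seen 0.50; mean among those seen 1/0.198 = 5.05 days.
- The last formula is symmetric in a and b. Median T 7 with median stay 5 gives 4.21 days, and so does median T 5 with median stay 7, although the true means are 10.1 and 7.2 days. In this model the summary responds to length of stay exactly as much as to clearance.

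**4. With 3-day labs (simulated; exponential T, lognormal stay with log-SD 0.5).**
- Median T 7 days, median stay 5, 7 and 10 days: mean among those seen 4.2, 5.0 and 6.1 days, with clearance unchanged.
- Median stay 7 days, median T raised from 5 to 14 days: the mean among those seen moves only from 4.7 to 5.5 days, while the full mean on the same lab grid moves from 8.8 to 21.7.

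**5. Central illustration (400,000 simulated patients).** T is lognormal, median 9 days, log-SD 0.7, so the true mean is 9 × exp(0.7²/2) = 9 × 1.278 = 11.5 days. Stay is lognormal, median 8 days, log-SD 0.5. The correlation of T and stay on the normal-score scale is 0 or 0.5.

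| Correlation | Seen to normalise | Mean among them | Shortfall from 11.5 |
|---|---|---|---|
| 0 | 35.6% | 7.3 days | 4.2 days |
| 0.5 | 30.1% | 7.8 days | 3.7 days |

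**6. Deaths.** If a random 10% or 20% never normalise, the proportion falls to 35.6 × 0.9 = 32.0% or 35.6 × 0.8 = 28.5% (correlation 0), and to 27.0% or 24.0% (correlation 0.5). The mean among normalisers stays at 7.3 and 7.8 days.

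**7. How far this depends on the assumptions.** Over 72 combinations (four distribution shapes; true median 6, 9 or 12; stay 6, 8 or 12; correlation 0 or 0.5) the mean among normalisers is below the true mean in 62, within 0.1 day in 3 and above it in 7, from 12.7 days low to 1.3 days high. Fast markers can go the other way: lognormal with median 3 days and stay 8 or 12 overstates the mean by 0.2 to 1.3 days, because detection waits for the next 3-day lab.

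**The case against.** The strongest reply is that the plan never promises a mean time. The thing to be evaluated in 1.2.2 is the labs, and the words about infusion and return to range can be read as a window. Section 11.2 offers profile plots for serial data, frequencies for a normalised yes/no, and an exploratory standard method that could include a survival analysis. This stands in part: a reader might infer that the plan commits to a mean among normalisers or excludes survival methods, and the documents support neither. It does not close the gap. The exploratory sentence names no method and no censoring or competing-event rule, and under the window reading the denominator and the handling of deaths and abnormal discharges are still unstated.

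A reader might also see a contradiction with section 9.0, where "All patients will be evaluated for response based on clinical outcomes and laboratory improvement". There is none: that sentence does not set the analysis set for 1.2.2, and improvement is not normalisation.

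Nor may one infer that the mean is always too low, or that the illustration estimates the error in this trial. Appendix 2 lists more than 20 labs, one assumed case cannot represent them, and a count over chosen combinations says nothing about likelihood. Finally, a mean over all patients could be formed by imputation, for example with the leaving date as the time; that rule is not stated and would be biased as well.

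**Conclusion.** The point holds as a minor one. The plan leaves open what the outcome of 1.2.2 is and which patients it counts. If it is taken as a time, the stated summary would rest on in-hospital normalisers only, barring an unstated imputation, and would be a poor guide to time to normalisation. In the assumed central case it is about 4 days below a true mean of 11.5 and uses about a third of patients; other assumptions give larger, smaller or reversed differences. The objective is secondary, and no test or decision rule hangs on it. The primary endpoint is not affected.

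**What to change.** Add to 11.2, for each marker:

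- The analysis set is all patients outside the institution's normal range at the infusion-day baseline.
- Report the number and proportion normalised by each scheduled 3-day lab and by discharge, with that full set as denominator.
- Show death, discharge and removal under 6.4/6.5 while still abnormal as separate counts.
- Show length of stay beside the proportions.
- Do not present a mean among normalisers as the time to normalisation.

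**Cost.** A few sentences and no special software. Appendix 2 already collects the infusion date and the date of discharge or death. Its printed lab table shows only name, result and units, and asks for a collection date only for the CoV PCR, so confirm that the electronic form stores a draw date for every result.

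**Downside.** The proportion describes in-hospital normalisation only and still depends on stay. With the same assumed clearance (lognormal, median 9 days), a median stay of 6 against 12 days moves it from 23% to 56% by discharge (correlation 0) or from 15% to 58% (correlation 0.5). By the day-6 lab it moves from 17% to 26%, or from 10% to 25%. That is why length of stay belongs next to it.

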4.0 PATIENT SELECTION

4.1 Eligibility Criteria

4.1.1 Diagnosis of SARS-CoV-2 infection via RT-PCR or FDA approved testing.

4.1.2 Patients must also have the following indications for enrollment:

- i. D-Dimer > 500 ng/ml FEU **OR**
- ii. IL-6 > 5 pg/mL

With any of the following

- iii. Lymphocytes < 0.8 10^3 /ul **OR**
- iv. LDH > 700 U/L **OR**
- v. CK > 170 U/L **OR**
- vi. CRP > 1.0 mg/dl **OR**
- vii. Ferritin > 1000 ng/ml

AND one of the following:

- viii. Age over 60 years
- ix. Underlying Active Malignancy
- x. Cardiovascular Disease
- xi. Active Tobacco Use
- xii. History of Pulmonary Volume Reduction Surgery
- xiii. Hypertension

4.1.3 Prior Treatment: Patients are still eligible for this trial if active antimicrobial agents are in use. Patients are also eligible if they had been treated on COVID-19 clinical trial in the course of their disease.

4.1.4 Age \geq 18 years.

4.1.5 The effects of allogeneic plasma infusion on the developing fetus is unknown. For this reason women who are pregnant are not eligible to participate.

4.1.6 Agrees to required laboratory data collected which will include the baseline organ function and regular ongoing assessments done as part of routine care.

4.1.7 Ability to understand and the willingness to sign a written informed consent document or ability to have consent provided by Legally Authorized Representative.

4.2 Exclusion Criteria:

4.2.1 Patients who do not meet above inclusion criteria are not eligible.

4.2.2 Patients may not be receiving any other investigational agents.

4.2.3 History of allergic reactions attributed to previous transfusion history.

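### Section 11.2 names mean and SD as the only numerical summary for all continuous variables; for laboratory markers likely to be right-skewed, it should add median, quartiles and within-patient ratios (minor)

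*Combined protocol and SAP*

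**What the plan says.** Section 11.2 sets the descriptive rule for the whole study: "mean and standard deviation for continuous variables; frequency for categorical variables". Nothing in the document names a median, quartiles, a range, a geometric mean or a log scale. The same paragraph states "No inferential statistical tests of hypotheses are planned". For repeated measures it adds that "individual as well as group profile plots will be generated to visualize the data", and it leaves one opening: "For exploratory purposes, standard statistical method will be used". On size it says only "The maximum projected accrual is 100 patients".

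The laboratory values appear elsewhere as follows.

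- The second secondary objective (1.2.2, repeated in 11.1) is "To measure normalization of laboratory parameters for risk as referenced in Appendix 2". It is assessed from infusion until the value is back within the institution's normal range.
- Section 9.0 judges response partly on laboratory improvement.
- Sections 6.6.1 and 10.0 and Appendix 2 provide a baseline on the day of planned infusion and a record every three days in hospital. The Appendix 2 form includes D-dimer, IL-6, CRP, LDH, CK and ferritin.
- Section 4.1.2 uses several of these markers as entry criteria, for example "D-Dimer > 500 ng/ml FEU" and "vii. Ferritin > 1000 ng/ml".

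**The concern.** Inflammatory and tissue-injury markers cannot go below zero and have no ceiling, so in acutely ill patients a long right tail is to be expected. The trial also expects some patients to progress to respiratory failure, septic shock or organ failure, because its primary endpoint counts them. Large upward values in a minority are therefore foreseeable.

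For such data the arithmetic mean follows the largest values. A table of means can show little or no fall, or even a rise, while most patients improve. The SD can exceed the mean, and the usual reading of mean minus one SD is then a negative concentration.

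With no hypothesis tests planned, the descriptive summaries are the trial's entire quantitative output, so the choice of summary decides what a reader learns about the laboratory course. Section 11.2 also names no numerical within-patient change, although each patient's infusion-day value and later values are recorded.

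**Working it through.** **Inputs.** From the documents: the summary rule and the maximum of 100 patients (11.2), and the marker list and cut-offs (4.1.2, Appendix 2). The documents give no SD, skewness or distribution for any marker and no sample-size calculation, so there is no figure of theirs to reproduce. Assumed for illustration: log-normal markers, with log-SD *s* between 0.5 and 1.5.

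**Step 1: skew at one time point.** For a log-normal variable, mean/median = exp(*s*²/2) and SD/mean = √(exp(*s*²) − 1).

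- *s* = 0.7: mean/median = exp(0.245) = 1.28; SD/mean = √(1.632 − 1) = 0.80.
- *s* = 1.0: mean/median = exp(0.5) = 1.65; SD/mean = √(2.718 − 1) = 1.31.
- *s* = 1.3: mean/median = exp(0.845) = 2.33; SD/mean = √(5.419 − 1) = 2.10.

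At *s* = 1.0 and 1.3 the SD exceeds the mean, so mean minus one SD is negative.

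**Step 2: change over time.** Let the typical patient's value fall by 30%, and let individual log-changes vary around ln 0.7 with SD *c*, independently of baseline. The expected ratio of means is 0.7 × exp(*c*²/2).

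- *c* = 0.5: 0.7 × 1.133 = 0.79, so the mean falls by about 21%.
- *c* = 1.0: 0.7 × 1.649 = 1.15, so the mean rises by about 15% although the median patient falls by 30%.

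The direction reverses at *c* = √(−2 ln 0.7) = √0.713 = 0.84. Simulation of 10,000 cohorts of 100 gave:

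| Baseline log-SD | Share of total held by top 5 of 100 | Cohort mean rises, *c* = 0.5 | Cohort mean rises, *c* = 1.0 |
|---|---|---|---|
| 0.5 | 12% | 0% | 82% |
| 1.0 | 25% | 0.6% | 74% |
| 1.5 | 41% | 3.2% | 64% |

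The median change was upward in under 0.5% of cohorts in every cell. As baseline spread grows, sampling noise moves both columns towards one half.

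This model lets the log-scale spread widen after baseline. If the markers were log-normal with the same log-scale spread at both times, the ratio of means would equal the ratio of medians (0.70), and the mean would not mislead on direction. The problem arises when most patients improve while some worsen sharply.

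**Step 3: the mechanism in its simplest form.** Suppose 90% of patients halve a marker and 10% rise fivefold, regardless of baseline. The expected ratio of means is 0.9 × 0.5 + 0.1 × 5 = 0.95, while the median patient's ratio is 0.50. This example is constructed to show the mechanism and is not an estimate.

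**Step 4: do the entry cut-offs cause the skew?** Take the extreme case in which every patient must exceed a cut-off placed at the marker's median. Then mean/median = [exp(*s*²/2) × Φ(*s*)/0.5] / exp(0.6745 *s*). At *s* = 1.0 this is 1.649 × 0.841 × 2 / 1.963 = 1.41. At *s* = 0.7 and 1.3 it is 1.21 and 1.75. All three are below the untruncated 1.28, 1.65 and 2.33, so a floor brings mean and median closer together.

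The actual rule imposes no such floor on any single marker. It asks for D-dimer or IL-6, with any one of five others. In a simulation of that rule under three assumed sets of marker medians, the share of eligible patients beyond the cut-off was 58% to 79% for D-dimer, 22% to 34% for LDH and 20% to 48% for ferritin.

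**The case against.** The strongest case against the point has four parts.

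1. **The plan does not rely on means alone.** Individual profile plots would show each patient's course, outliers included, and exploratory methods are allowed. This stands in part: the typical change is not hidden from someone who studies the plots. However, plots for up to 100 patients on some twenty laboratory values do not replace a sound table, and the clause on exploratory methods commits to nothing.

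2. **The stated laboratory objective is already within-patient and anchored at infusion.** Whether and when a value normalises is not driven by a few extreme concentrations. This stands. Mean marker level is not a named endpoint, and the first secondary objective is serial PCR. A reader might infer that the laboratory course is the trial's main pharmacodynamic evidence, or that 11.2 prescribes tables of means by visit. The document says neither.

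3. **The size is assumed.** This stands. With a log-change SD of 0.5 the mean almost never moves the wrong way, and the result also depends on the spread widening after baseline.

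4. **Later visits include only patients still in hospital.** A visit-by-visit median would therefore not describe the whole cohort either. This stands and is met in the fix by reporting counts.

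A reader might also infer that the entry cut-offs truncate several markers from one side and so create the problem. The criteria do not support that. They are alternatives, so a patient who qualifies on IL-6 and CRP may have any D-dimer, LDH, CK or ferritin. Even a strict floor would lower the mean-to-median ratio.

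**Conclusion.** The point holds as a minor one. Mean and SD are the only numerical summary that 11.2 names, and they suit poorly those laboratory markers that are likely to be right-skewed. The cause is the skew itself. The entry criteria enrich for abnormal values but do not produce it.

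The consequence can range from negligible to a reversed direction of change, depending on how widely individual responses vary. Under the independence model, the mean starts to point the wrong way when the log-change SD passes about 0.84. Nothing in the documents shows on which side of that value this cohort would lie.

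It would go too far to say that the plan conceals the patients' course or that a trial conclusion fails. The primary endpoint is binary and summarised by frequency, no test or sample size depends on a marker mean, and individual profiles will be drawn. What remains is that the tabulated laboratory results could misrepresent the typical patient, in a trial that reports only descriptive results and counts laboratory improvement towards response.

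**What to change.** Amend 11.2, before results are seen, to say in substance:

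- For laboratory markers likely to be right-skewed (D-dimer, IL-6, CRP, LDH, CK, ferritin), report median and quartiles. Mean and SD may be kept alongside, and remain adequate for roughly symmetric variables such as sodium or haemoglobin.
- Summarise change as each patient's ratio to his or her own infusion-day value, using the median ratio or the geometric mean ratio.
- Draw the profile plots for these markers on a log axis.
- At each time point, state how many patients are still in hospital and how many were measured.

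The cost is a few sentences of analysis wording and slightly longer tables. No new data, patients or procedures are needed, because the baseline and three-day values are already recorded.
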